3. INTRODUCTION

The purpose of this document is to provide a more technical and detailed elaboration of the principal features of the analysis than was described in the protocol, and to include detailed procedures for executing the statistical analysis of the primary and secondary endpoints and other data.

This TSAP assumes familiarity with the Clinical Trial Protocol (CTP), including Protocol Amendments. In particular, the TSAP is based on the planned analysis specification as written in CTP Section 7 “Statistical Methods and Determination of Sample Size”. Therefore, TSAP readers may consult the CTP for more background information on the study, e.g., on study objectives, study design and population, treatments, definition of measurements and variables, planning of sample size, randomization.

R version 3.6.1 with “DoseFinding” package ([1](#)) will be used for analysis based on MCPMod.

SAS® Version 9.4 (or later version) will be used for all other analyses.

4. CHANGES IN THE PLANNED ANALYSIS OF THE STUDY

The primary endpoint, Complete Renal Response (CRR), as defined in the CTP, is derived from urine protein (UP) determined from the 24-hour (24h) urine collections and eGFR calculated from serum creatinine. To account for incomplete 24h collections, an alternate derivation of CRR is added with this version of the TSAP. The alternate derivation is based on the ratio of urine protein/urine creatinine (UP/UC) determined from the 24h collections and eGFR calculated from serum creatinine. This alternate derivation will be analysed and presented using the same methods/format used for CRR derived from UP, as adjustment for UC is considered an important correction for incomplete collections. See [Section 6.6.1](#) for further details.

The definition for the secondary endpoint, major renal response (MRR), specified in the CTP was incomplete. See [Section 5.2](#) for a revision affecting only patients who entered the trial with baseline proteinuria ≥ 3 g/day. There is no change for patients who entered the trial with baseline proteinuria < 3 g/day.

Alternate derivations of PRR & MRR based on UP/UC determined from the 24h urine collections and eGFR calculated from serum creatinine are also added with this version of the TSAP. As with CRR, the alternate PRR & MRR derivations will be analyzed and presented using the same format as used for derivations using UP.

A second alternate derivation of CRR is based on UP/UC as determined from the spot urines and eGFR calculated from serum creatinine. This allows defining CRR based on the samples collected at Weeks 1, 2, 4, 6, 8, 12, 16, 21, 26, 30, 35, 40, 46 and 52. For comparison to the derivations based on the 24h samples, observed proportions at Weeks 26 and 52 were tabulated and pairwise comparisons of each dose to placebo were performed.

Important Protocol Deviations (iPDs) and populations for analysis were updated to reflect learnings and input from Key Opinion Leaders (KOLs).

The logistic regression model specified in the CTP included one of the two stratification variables used at randomization as a covariate, namely race (Asian/non-Asian). The other stratification variable used for the randomization was proteinuria at screening. Proteinuria at screening $<3\text{g/day}$ or $\geq 3\text{g/day}$ (respectively $\text{UP/UC} < 3$ or $\text{UP/UC} \geq 3$) was added to the model as a covariate via the TSAP.

5. ENDPOINT

5.1 PRIMARY ENDPOINT

The primary endpoint is the proportion of patients with CRR at week 52, where CRR is defined as:

UP<0.5 g/d at week 52

and either

eGFR within normal range at week 52

or

decrease in eGFR<20% from baseline at week 52 if eGFR is below normal range (i.e., below Lower Limit of Normal, where LLN =90 ml/min)

For the assessment of proteinuria for the primary and secondary endpoints, 24h urine collection was performed at baseline, 26 and 52 weeks. Collection was performed in duplicate (2 times 24h collection). The value of proteinuria is the average of the two values. Blinded review of the volumes of the 24h collections and durations of collection raised concern that some collections may have been incomplete. It was decided that the 24h samples should be $\geq 500\text{mL/day}$ and at least 19.5 hours (approximately 80% of 24 hours) to be evaluable. With respect to UP, any collections $< 500\text{mL/day}$ or < 19.5 hours were not evaluated.

Rules for deriving UP from 24h urine collections to determine CRR

Protein excretion rates were transferred to BI in units of mg/dL. The following steps were performed to convert to g/day for deriving CRR.

Protein excretion rate (mg/dL) x 1/100 = Protein excretion rate (mg/ml)

Protein excretion rate (mg/ml) x 24-hour total volume (ml) = UP (mg)

UP (mg) * 1/1000= UP (g/day)

After the interim analysis the team had concerns around how well the thresholds ($\geq 500\text{mL/day}$ and at least 19.5 hours) set for evaluability compensated for incomplete 24h collections. Another method to account for incomplete 24h collections was introduced and CRR was also derived based on the ratio of urine protein/urine creatinine (UP/UC) determined from the 24h collections. As the total amount of creatinine excreted daily in the urine is quite stable, UC is used to stabilize the estimate of proteinuria and is generally accepted as a correction for incomplete collections. With this version of the TSAP, this alternate derivation is incorporated. CRR derived using the UP/UC determination will be analysed and presented using the same methods/format used for CRR derived from UP. There is no change to the eGFR component of the definition; it will be calculated from serum creatinine as defined in the CTP.

Another alternate derivation of CRR is to base it on UP/UC as determined from the spot urines (and eGFR calculated from serum creatinine.) This allows defining CRR based on the samples collected at Weeks 1, 2, 4, 6, 8, 12, 16, 21, 26, 30, 35, 40, 46 and 52. For comparison to the derivations based on the 24h samples, observed proportions at Weeks 26 and 52 were tabulated and pairwise comparisons of each dose to placebo were performed.

Proprietary confidential information © 2020 Boehringer Ingelheim International GmbH or one or more of its affiliated companies

One of the KOLs consulted, suggested an assessment of how the eGFR threshold for patients below the lower limit of normal (LLN) affected determination of CRR. The suggestion was to allow less of a decrease (10%) in eGFR for those patients below the lower limit of normal (LLN) to achieve CRR compared to the protocol-allowed decrease of 20%.

Rules for imputing missing data or data that was not evaluable are provided in [Section 6.6.1](#). Also specified in Section 6.6.1 are rules for defining CRR for patients who discontinued study medication and/or participation in the trial.

5.2 SECONDARY ENDPOINTS

5.2.1 Key secondary endpoint

This section is not applicable as there is no key secondary endpoint.

5.2.2 Secondary endpoints

- Proportion of patients with CRR at week 26
- Proportion of patients with partial renal response (PRR) at week 26 and week 52.

PRR is defined as at least 50% reduction of proteinuria from baseline if eGFR within normal range at time of assessment or decrease of eGFR < 20% from baseline if eGFR below normal range at time of assessment.

- Proportion of patients with major renal response (MRR) at week 26 and 52

MRR is defined as follows depending on proteinuria at baseline:

- If baseline proteinuria < 3 g/day **and** patient has CRR
- If baseline proteinuria ≥ 3 g/day **and** proteinuria < 1g/day

and either

eGFR within normal range

or

decrease in eGFR < 20% from baseline at week 26 if eGFR is below normal range (below Lower Limit of Normal, where LLN = 90 ml/min)

The secondary endpoints, CRR at week 26, PRR at week 52 and MRR at week 52 will be derived using UP and using UP/UC from the 24h collections, each along with eGFR determined from serum creatinine

Proprietary confidential information © 2020 Boehringer Ingelheim International GmbH or one or more of its affiliated companies

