5.2 ASSESSMENT OF EFFICACY

Assessment of Renal Response:

For primary and secondary efficacy endpoints at baseline (week 0), week 26 and 52, 24h collection of urine will be performed in duplicates (2 times 24 h collection).

A detailed description for urine collection will be provided in the laboratory manual and instructions provided to the patients. At other time points, proteinuria will be assessed by spot urine.

Complete and partial renal responses are defined as follows:

- Complete renal response (CRR) is defined as Uprot <0.5 g/day and eGFR within normal range; or decrease <20% from baseline if below normal range. Non responder patients withdrawn at 6 months are considered non responders for the 26 and 52 week timepoint for the primary endpoint.
- Partial renal response (PRR) is defined as 50% reduction of proteinuria from baseline and eGFR within normal range or decrease < 20% from baseline if below normal range.
- Major renal response (MRR) is defined as :
 - if baseline proteinuria <3 g/day : CRR at week 52
 - if baseline proteinuria \geq 3 g/day : proteinuria <1g/day at week 52.

Renal biopsies:

Renal biopsies slides or electronic files used for the diagnosis as described in inclusion criterion have to be available as biopsies are planned to be re-assessed centrally by one pathologist for retrospective analysis. An additional renal biopsy at the end of treatment is voluntary. The renal biopsy at the end of treatment may provide additional information on remaining activity or chronicity of the renal damage despite clinically low disease activity ([R15-3725](#)). Change in renal biopsy at week 52 compared to screening biopsy (only for patients with a biopsy at the end of treatment (See [section 5.2](#))) will be evaluated.

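### The SAP's wording of partial renal response can be read as dropping the proteinuria requirement when eGFR is below normal

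*SAP*

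**What the plan says.** Protocol 5.2 defines the endpoint in one sentence: "Partial renal response (PRR) is defined as 50% reduction of proteinuria from baseline and eGFR within normal range or decrease < 20% from baseline" when eGFR is below normal. The proteinuria fall and the eGFR condition are joined by *and*.

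SAP 5.2.2 uses *if* instead. Its first half is "PRR is defined as at least 50% reduction of proteinuria from baseline if eGFR within normal range at time of assessment or decrease of eGFR"; the part after *or* is "decrease of eGFR < 20% from baseline if eGFR below normal range at time of assessment". Each half carries its own condition on eGFR.

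The SAP builds its other response definitions differently. For complete renal response (CRR), SAP 5.1 states the proteinuria threshold, then *and either* normal eGFR *or* "decrease in eGFR<20% from baseline at week 52 if eGFR is below normal range (i.e., below Lower Limit of Normal, where LLN =90 ml/min". SAP 5.2.2 uses the same structure for major renal response (MRR) in patients with baseline proteinuria of 3 g/day or more.

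SAP section 4 declares a revised definition for MRR only: "The definition for the secondary endpoint, major renal response (MRR), specified in the CTP was incomplete". For PRR it adds a urine protein/creatinine (UP/UC) version and says that "the alternate PRR & MRR derivations will be analyzed and presented using the same format as used for derivations using UP". The SAP history table describes the July 2017 edit to PRR as a clarification.

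PRR at weeks 26 and 52 is a secondary endpoint. SAP 7.5.2 compares each dose with placebo on observed proportions, in the ITT and per-protocol sets.

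**The concern.** With one condition on each side of *or*, the most literal parse is two parallel routes to response: a proteinuria fall for patients with normal eGFR, and a stable eGFR for patients below normal. The second route makes no demand on proteinuria. A patient whose proteinuria is unchanged or rising would count as a partial responder because eGFR is low but stable.

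This is the only definition of PRR in the SAP text available for review, and SAP 6.6.1 adds imputation and discontinuation rules without restating it. Two competent programmers could derive different PRR data sets from the sentence. At stake are the PRR rates in every arm and their differences from placebo.

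**Working it through.** **1. The two readings as logic.** Let P = proteinuria down by at least 50%; N = eGFR normal (at least 90, from the lower limit in SAP 5.1); S = eGFR below 90 with a decrease of less than 20%.

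- Protocol, natural reading: P and (N or S).
- SAP, literal reading: (P and N) or S.

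The first expands to (P and N) or (P and S), which lies inside the second. The literal reading therefore adds exactly the patients with S but not P, and no arm's rate can fall.

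**2. Example records.**

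| Proteinuria, g/day | eGFR | Protocol | SAP literal |
|---|---|---|---|
| 3.0 to 1.2 | 100 to 98 | yes | yes |
| 3.0 to 1.2 | 70 to 68 | yes | yes |
| 3.0 to 2.9 | 70 to 68 | no | yes |
| 3.0 to 3.6 | 60 to 62 | no | yes |

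**3. Can such patients be in the trial?** Yes. Protocol 3.3.3 excludes only GFR below 30 at screening, so eGFR of 30 to 89 is eligible. The documents do not give the expected share.

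**4. The plan's own figure.** None is stated for PRR. The 82% success probability in Protocol 7.7 is for CRR (scenario Expected A, 40:20:20:40). An MCPMod simulation of that scenario gave 83.0%, 83.4% and 84.2% under three guessed sets of candidate-model parameters, which broadly reproduces it. It does not depend on PRR.

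**5. Size if the literal text is programmed.** Inputs per arm:

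- f = share with eGFR below 90 at assessment. Assumed 0.2 to 0.6.
- s = share of those with a decrease of less than 20%. Assumed 0.8 in both arms here.
- q = probability of P. Assumed 45% on placebo and 65% on drug. The 45% is the middle of 40 to 50%, from the 20-30% complete plus about 20% partial response in Protocol 2.1. That is a renal response rate used as a stand-in for a proteinuria fall. The 65% has no source in the documents.
- P taken as independent of eGFR.

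Protocol reading = (1 − f)q + f·s·q. Literal reading = (1 − f)q + f·s. Added responders = f·s·(1 − q).

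For f = 0.4 on placebo: protocol 0.6×0.45 + 0.4×0.8×0.45 = 0.414; literal 0.6×0.45 + 0.4×0.8 = 0.590; added 0.176.

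| f | Placebo, protocol → literal | Drug, protocol → literal | Difference, points |
|---|---|---|---|
| 0.2 | 43.2% → 52.0% | 62.4% → 68.0% | 19.2 → 16.0 |
| 0.4 | 41.4% → 59.0% | 59.8% → 71.0% | 18.4 → 12.0 |
| 0.6 | 39.6% → 66.0% | 57.2% → 74.0% | 17.6 → 8.0 |

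Placebo rises by 8.8, 17.6 and 26.4 points.

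**6. Direction.** With equal f, the difference shrinks only if placebo gains more responders than drug, that is if s₀(1 − q₀) > s₁(1 − q₁). For q of 45% and 65% this needs s₀/s₁ > 0.35/0.55 = 0.64; for 45% and 55% it needs s₀/s₁ > 0.45/0.55 = 0.82.

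If the drug also protects eGFR (s₀ = 0.6, s₁ = 0.9; q 45% and 55%), the difference grows. At f = 0.4, placebo goes from 37.8% to 51.0% and drug from 52.8% to 69.0%, so 15.0 points become 18.0. At f = 0.6, 17.5 become 22.0.

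**The case against.** The SAP sentence has a second reading: at least a 50% fall, provided that eGFR is normal or, when below normal, has decreased by less than 20%. That matches the protocol. The protocol sentence is not watertight either. It has the form A *and* B *or* C without brackets, and strict operator precedence would give it the same meaning as the literal SAP text. The history table's word for the edit, the absence of any declared change of meaning, and SAP 6.6.1's description of secondary endpoints as based on proteinuria and eGFR all point to an unclear sentence. A reader might infer that the SAP deliberately redefined PRR, or that PRR has been scored wrongly. The documents support neither, and nothing in the text reviewed shows how PRR was programmed. This part of the objection stands. It does not remove the fault, because the SAP is where the ambiguity has to be settled.

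A reader might also infer that false responders arise about equally in all arms and so must dilute the drug effect. Equal additions would leave the absolute difference unchanged. Dilution occurs only when placebo gains more, and the documents give no eGFR figures by arm from which to know that.

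The size is weakly anchored. The 45% may already include an eGFR criterion, which the formula then applies again. SAP 6.6.1 also makes non-responders of patients who stop for lack of efficacy or are treated for less than 46 weeks, which limits the inflation.

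Finally, there is no key secondary endpoint, the trial is exploratory, and PRR p-values are nominal. This limits the consequence.

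**Conclusion.** The point holds as a drafting fault. On its most literal parse, the SAP's PRR definition has no proteinuria requirement for patients with below-normal eGFR. That departs from the natural reading of Protocol 5.2 and from the SAP's own structure for CRR and MRR.

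The consequence is conditional on the literal text being programmed. It is then certain that PRR rises or stays the same in each arm. The placebo rise of about 9 to 26 points is an illustration that rests on the assumed f, s and q and on independence. If patients with stable eGFR are also more likely to have the proteinuria fall, the rise is smaller. The dose-placebo difference would be distorted in a direction that the documents do not determine. The primary CRR analysis and the 82% figure do not change. The point should be corrected, but it does not threaten the trial's main conclusion.

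**What to change.** Replace the PRR sentence in SAP 5.2.2 with one in the form already used for CRR, for example:

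> PRR requires a fall in proteinuria of at least 50% from baseline AND either (a) eGFR within normal range at the time of assessment OR (b) if eGFR is then below normal range (LLN = 90 ml/min), a decrease in eGFR of less than 20% from baseline.

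Copy only the structure from MRR. Its eGFR limb reads "decrease in eGFR < 20% from baseline at week 26 if eGFR is below normal range", although MRR is assessed at weeks 26 and 52.

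Then confirm that the derivation program requires the proteinuria fall in both eGFR branches, at weeks 26 and 52, for every PRR derivation used. SAP 5.2.2 names only week 52 when it lists PRR under both UP and UP/UC, and section 4 names no week for the added UP/UC version, so the revised text should also say whether UP/UC applies at week 26. Record the edit as a clarification that restores the protocol's meaning.

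The cost is one sentence and a code check, with no new data. Relative to the literal text, reported PRR rates can only fall or stay the same.

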Definition/derivation of CRR for patients who prematurely stop trial medication

The rules below will be applied to derive CRR/PRR/MRR for the ITT:

Proprietary confidential information © 2020 Boehringer Ingelheim International GmbH or one or more of its affiliated companies

- (1) If the reason for discontinuation of treatment is ‘Lack of efficacy’ or AE type is ‘Worsening of disease under study’, then CRR will be defined as ‘Non-responder’.
- (2) If the patient used prohibited meds known to impact CRR following discontinuation of study med, then CRR will be defined as ‘Non-responder’.
- (3) If neither #1 or #2 apply and treatment duration ≥ 46 weeks, then use the lab data collected at Visit 16-EOT/Week 52 to derive the endpoints. If there is no lab data at Visit 16-EOT /Week 52, then use the lab data closest to 52 weeks that is within 6 weeks prior to week 52.
- (4) If neither #1 or #2 apply and treatment duration < 46 weeks, then CRR will be defined as ‘Non-responder’.

Note that patients handled with the above rules are included in the ITT population. They would only be included in the PPS if they complete 46 weeks of the treatment regimen.

For patients who took study drug for < 46 weeks, continued to participate in the trial and have urine collections and serum creatinine determinations, their data will be displayed in a listing.

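### The SAP ties the eGFR-decrease condition of major renal response to week 26 although MRR is also a week-52 endpoint; a smaller gap is that the early-stop rules do not name their visit

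*SAP*

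**What the plan says.** SAP 5.2.2 lists the "Proportion of patients with major renal response (MRR) at week 26 and 52" and gives one definition for both visits. It then confirms that "PRR at week 52 and MRR at week 52 will be derived using UP", and by UP/UC as well. Patients with baseline proteinuria below 3 g/day need CRR. Patients at or above 3 g/day need proteinuria below 1 g/day and either a normal eGFR or, in the SAP's words, "decrease in eGFR < 20% from baseline at week 26 if eGFR is below normal range". The lower limit of normal is 90 ml/min. No week-52 counterpart of that condition is given.

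The neighbouring endpoints are worded differently. PRR, in the same section, allows a "decrease of eGFR < 20% from baseline if eGFR below normal range at time of assessment". The primary CRR in SAP 5.1 asks for a "decrease in eGFR<20% from baseline at week 52 if eGFR is below normal range".

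SAP 4 calls the protocol's MRR definition incomplete and points to section 5.2 "for a revision affecting only patients who entered the trial with baseline proteinuria" of at least 3 g/day. In Protocol 5.2 that branch has a week-52 proteinuria criterion and no eGFR condition.

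SAP 6.6.1 has four rules for patients who stop trial medication early, introduced as deriving CRR, PRR and MRR in the ITT set. Rules 1 (lack of efficacy or worsening disease) and 2 (prohibited medication after discontinuation) make CRR a non-response and name no visit. Rule 3 (at least 46 weeks on treatment) uses week-52 laboratory data, or data from the 6 weeks before, for the endpoints. Rule 4 reads "If neither #1 or #2 apply and treatment duration < 46 weeks, then CRR will be defined as" a non-response, again without a visit. The week-21/26 spot-urine imputation stands under the heading for patients who do not stop early.

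**The concern.** The SAP is the only source for the eGFR condition in the ≥3 g/day branch of MRR, and it names the wrong visit for one of the two MRR endpoints. A programmer who follows the sentence judges week-52 MRR on renal function six months out of date. One who follows the evident intent uses week-52 eGFR. The two can disagree in either direction.

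The early-stop rules raise a lesser version of the same problem. CRR, PRR and MRR are all week-26 endpoints too, yet no rule says what happens at week 26 to a patient who later stops. SAP 7.5.2 plans pairwise Barnard tests and Newcombe intervals for the secondary endpoints, and further week-26 CRR analyses by race and by screening proteinuria, so the classification is used.

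**Working it through.** The plan has no figure to reproduce here. The check sets the texts side by side and then uses invented patients to show what the wording does.

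**Step 1: the visit attached to the eGFR-decrease condition**

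| Endpoint | Visits | eGFR decrease judged at |
|---|---|---|
| Primary CRR (SAP 5.1) | 52 | week 52 |
| PRR (SAP 5.2.2) | 26 and 52 | time of assessment |
| MRR, baseline ≥3 g/day (SAP 5.2.2) | 26 and 52 | week 26 |

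Only MRR has a mismatch between the visits listed and the visit named.

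**Step 2: who is reached.** The readings can differ at week 52 only for patients with baseline proteinuria ≥3 g/day, week-52 proteinuria below 1 g/day and week-52 eGFR below 90. Everyone else is settled by another part of the definition.

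**Step 3: two illustrative patients (assumed values).** Both have baseline proteinuria ≥3 g/day, week-52 proteinuria 0.8 g/day and baseline eGFR 80. The condition fails when eGFR is 0.8 × 80 = 64 or lower. Change = follow-up / baseline − 1.

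| | eGFR wk 26 | Change | eGFR wk 52 | Change | Wk-52 MRR, literal | Wk-52 MRR, on wk-52 eGFR |
|---|---|---|---|---|---|---|
| A | 76 | 76/80 − 1 = −5.0% | 55 | 55/80 − 1 = −31.25% | responder | non-responder |
| B | 60 | 60/80 − 1 = −25.0% | 78 | 78/80 − 1 = −2.5% | non-responder | responder |

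The classification reverses in both.

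**Step 4: rule 4 and week 26.** The cut-off is 52 − 6 = 46 weeks, which matches the 6-week look-back in rule 3. Rules 3 and 4 are complements (≥46 and <46 weeks), so the set is built around week 52. Read literally for week 26, rule 4 matters for patients with an observed on-drug week-26 response who stop between visit 11 (week 26, day 183) and week 46 (day 323). That is 323 − 183 = 140 days = 20 weeks, or 20/52 = 38% of the treatment period. This is a share of calendar time, not of patients. Patients treated for less than 46 weeks are not in the per-protocol set, so this part concerns the ITT analyses only.

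**Step 5: size.** One recoded patient is 1/20 = 5.0 points or 1/40 = 2.5 points at the planned arm sizes. For rule 4, shift in the week-26 rate = share of the arm stopping in the window × week-26 response among them. The documents give neither input. Assuming 5% to 20% stopping and 25% to 45% response, the shift runs from 0.05 × 0.25 = 1.25 points to 0.20 × 0.45 = 9.0 points. There is no basis in the documents for a corresponding range on the MRR wording, because the eGFR distribution is not given.

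**The case against.** The strongest reply is that the MRR wording is an evident slip. The other parts of the branch carry no visit, PRR a few lines above is worded correctly, and the protocol ties MRR to week 52. Few statisticians would pair week-52 proteinuria with week-26 eGFR on purpose. That stands as a statement of intent. It does not make the text right, and the protocol cannot supply the missing condition because it has none for this branch.

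On the early-stop rules more of the reply stands. A reader might infer that PRR and MRR have no early-stop outcome because rules 1, 2 and 4 name CRR only. The documents do not support that: the lead-in covers all three endpoints, and rule 3 refers to them together. Naming all three would only clarify.

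It can also be argued that the protocol already settles week 26. Protocol 7.5 counts non-completers as failures for primary and secondary endpoints, and Protocol 6.2.3.1 uses completer for week 52, so anyone stopping before then would fail at week 26 too. But Protocol 7.5 does not say at which visit completion is judged, and on that reading rule 3, which accepts stops from week 46 on, would already depart from it. Protocol 5.2 does mention both time points, and its mention of week 26 makes sense only for CRR at that visit. However, it concerns non-responders withdrawn at 6 months and is worded for the primary endpoint. It does not reach a week-26 responder who stops later.

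Finally, the interim plan and the code in SAP 9.1 are not in the public text and may resolve these points. This review can speak only to the text available.

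**Conclusion.** The MRR sentence is wrong as written and should be corrected: followed literally, it can misclassify week-52 MRR in either direction in the subgroup described in Step 2. The early-stop gap is real but smaller. The rules are plainly meant for week 52, but they do not say so, and week 26 is left without a stated rule for patients who stop early.

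The reach is limited. On key secondary endpoints the SAP states: "This section is not applicable as there is no key secondary endpoint". The affected endpoints are therefore exploratory secondary ones. A reader might infer that the primary result is at risk; it is not, because the primary CRR condition names week 52 and the early-stop rules fit that visit. A reader might also infer a bias for or against BI 655064. Nothing in the documents shows that affected patients would fall unevenly across arms, and none is claimed.

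The size is unknown. The per-patient shifts assume the planned arm sizes, and the eGFR values, stopping shares and response rates above are illustrations, not estimates.

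**What to change.** 1. In SAP 5.2.2, replace the reference to week 26 in the MRR eGFR-decrease condition with the time-of-assessment wording used for PRR. This applies to both the UP and the UP/UC derivation.
2. In SAP 6.6.1, state that the four early-stop rules, including the 46-week cut-off, define week-52 CRR, PRR and MRR. Naming all three in rules 1, 2 and 4 is a helpful clarification.
3. In the same section, state how early stoppers are classified at week 26, after reconciling this with the non-completer rule in Protocol 7.5 and the six-month non-responder rule in Protocol 5.2. The text should cover stops before visit 11, stops at visit 11 (an end-of-treatment timing that Protocol 6.2.3.3 uses as an example) and stops between weeks 26 and 46. Whether an on-drug week-26 response survives a later stop is a choice of estimand on which statisticians can differ. The request is that the sponsor state its choice, not that it adopt a particular one.

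The cost is one phrase in 5.2.2, a few sentences in 6.6.1 and a small programming check. No new data are needed, and no sample size or power figure changes.
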